6.0 Registration/Randomization Procedures

6.1 Phase I

Prior to discussing protocol entry with the patient, call the MCCC Registration Office [contact]) for dose level and to insure that a place on the protocol is open to the patient.

- 6.11 Registration Procedures
 - 6.111 To register a patient, [contact]) a completed eligibility checklist to the Mayo Clinic Cancer Center (MCCC) Registration Office between 8 a.m. and 4:30 p.m. central time Monday through Friday.

6.2 Phase II

- 6.21 Registration Procedures
 - 6.211 To register a patient, access the Mayo Clinic Cancer Center (MCCC) web page and enter the registration/randomization application. The registration/randomization application is available 24 hours a day, 7 days a week. Back up and/or system support contact information is available on the Web site. If unable to access the Web site, call the MCCC Registration Office at [contact] between the hours of 8 a.m. and 5:00 p.m. Central Time (Monday through Friday).

The instructions for the registration/randomization application are available on the MCCC web page

(http://hsrwww.mayo.edu/ccs/training) and detail the process for completing and confirming patient registration. Prior to initiation of protocol treatment, this process must be completed in its entirety and a MCCC subject ID number must be available as noted in the instructions. It is the responsibility of the individual and institution registering the patient to confirm the process has been successfully completed prior to release of the study agent. Patient registration via the registration/randomization application can be confirmed in any of the following ways:

- Contact the MCCC Registration Office [contact]. If the patient was fully registered, the MCCC Registration Office staff can access the information from the centralized database and confirm the registration.
- Refer to "Instructions for Remote Registration" in section "Finding/Displaying Information about A Registered Subject."

6.3 Phase I and II

6.31 Correlative Research

Mandatory

A mandatory correlative research component is part of this study, the patient will be automatically registered onto this component (see Sections 3.19c and 17.0).

Optional

An optional correlative research component is part of this study: there will be an option to select if the patient is to be registered onto this component (see Section 17.0).

- Patient has/has not given permission to give his/her *tissue* sample for research testing as a part of this study (see section 17.0).
- 6.32 Prior to accepting the registration, registration/randomization application will verify the following:
 - IRB approval at the registering institution
 - Patient eligibility
 - Existence of a signed consent form
 - Existence of a signed authorization for use and disclosure of protected health information
- 6.33 Documentation of IRB approval must be on file in the Registration Office before an investigator may register any patients.

In addition to submitting initial IRB approval documents, ongoing IRB approval documentation must be on file (no less than annually) at the Registration Office ([contact]). If the necessary documentation is

not submitted in advance of attempting patient registration, the registration will not be accepted and the patient may not be enrolled in the protocol until the situation is resolved.

When the study has been permanently closed to patient enrollment, submission of annual IRB approvals to the Registration Office is no longer necessary.

- 6.34 At the time of registration, the following will be recorded:
 - Patient has/has not given permission to store and use his/her sample(s) for future research of Non-small cell lung cancer at Mayo.
 - Patient has/has not given permission to store and use his/her sample(s) for future research to learn, prevent, or treat other health problems.
 - Patient has/has not given permission for MCCC to give his/her sample(s) to researchers at other institutions.
- 6.35 Treatment on this protocol must commence at Mayo Clinic Arizona institution under the supervision of a medical oncologist.
- 6.36 Treatment cannot begin prior to registration and must begin \Box 14 days after registration.
- 6.37 Pretreatment tests/procedures (see Section 4.0) must be completed within the guidelines specified on the test schedule.
- 6.38 All required baseline symptoms (see Section 10.3) must be documented and graded.

7.0 Protocol Treatment

7.1 Treatment Schedule

7.11 Phase I Cohort:

| Agent | Dose Level | Route | Day | ReRx |
|-----------|---------------------|-------|-----------------------------------|------|
| Auranofin | As assigned by | PO | PO Daily | |
| | Registration office | | | days |
| Sirolimus | 5 mg | PO | Daily (cycle 1 only, begin day 8, | Q28 |
| | | | subsequent cycles begin day 1) | days |

7.12 Phase 2 Cohort (at MTD from Phase I):

| Agent | Dose Level | Route | Day | ReRx |
|-----------|--------------------|-------|-----------------------------------|------|
| Auranofin | As determined by | PO | Daily | Q28 |
| | studies in Phase I | | | |
| Sirolimus | olimus 5 mg PO | | Daily (cycle 1 only, begin day 8, | Q28 |
| | | | subsequent cycles begin day 1) | days |

7.2 Phase I Dose Escalation and Determination of MTD

7.21 Dose Escalation Guidelines

| Dose Level | Auranofin |
|------------|------------|
| 0* | 3 mg daily |
| 1 | 6 mg daily |

^{*} Starting dose level.

- 7.211 Three patients will be treated at each dose level and observed for a minimum of 1 cycle, to assess toxicities, before new patients are treated.
- 7.212 Investigators are to contact the Study Chair as soon as any dose-limiting toxicity occurs.
- 7.213 For this protocol, dose-limiting toxicity (DLT) will be defined as an adverse event attributed (definitely, probably, possibly) in the first cycle to the study treatment and meeting the following criteria:

| Toxicity | DLT Definition |
|-------------|--------------------------|
| Hematologic | Grade 4 Neutropenia |
| | Grade 4 Thrombocytopenia |
| Non- | ≥Grade 3 Anaphylaxis |
| hematologic | |
| | ≥Grade 3 Proteinuria |
| | |
| | ≥Grade 3 Hematuria |
| | ≥Grade 3 Rash acneiform |
| | ≥Grade 3 Diarrhea |
| | ≥Grade 3 Mucositis oral |

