7.22 MTD Determination

MTD is defined as the dose level below the lowest dose that induces doselimiting toxicity in at least one-third of patients (at least 2 of a maximum of 6 new patients).

7.221 Three patients will be treated at a given dose level combination and observed for at least 1 cycle to assess toxicity (accrual will be suspended while the 3 patients are treated and observed).

- 7.222 If dose-limiting toxicity (DLT) is not seen in any of the 3 patients, 3 new patients will be accrued and treated at the next higher dose level. If DLT is seen in 2 or 3 of 3 patients treated at a given dose level, then the next 3 patients will be treated at the next lower dose level, if only 3 patients were enrolled and treated at this lower dose level.
- 7.223 If DLT is seen in 1 of 3 patients treated at a given dose level, up to 3 additional patients will be enrolled and treated at the same dose level (accrual will be suspended while the 3 patients are treated and observed). If DLT is seen in at least one of these additional three patients (≥2 of 6), the MTD will have been exceeded and further accrual will cease to this cohort. If DLT is not seen in any of the three additional patients, 3 new patients will be accrued and treated at the next higher dose level.
- 7.224 After enrolling 6 patients on a specific dose level, if DLT is observed in at least 2 of 6 patients, then the MTD will have been exceeded and defined as the previous dose unless only 3 patients were treated at the lower dose level. In that case, 3 additional patients will be treated at this lower dose level.
- 7.23 Dose Escalation: Doses will not be escalated in any individual patient.
- 7.24 If a patient fails to complete Cycle 1 for reasons other than toxicity, the patient will be regarded as treatment intolerant and an additional patient will be treated at the current dose level.
- 7.3 Patients can be instructed in administration techniques for both sirolimus and auranofin and granted treatment independence.
- 7.4 Patient must return to Mayo Clinic for evaluation at least every week during the first cycle of treatment and then at least every 4 weeks.
- 7.5 Study treatment by a local medical doctor (LMD) is not allowed.

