16.11 Phase I Study

This run-in phase I study is a cohorts of 3 design. For a subject to be considered evaluable for dose-limiting toxicity (DLT) the subject must have received at least one dose of each drug in Cycle 1. If a subject withdraws from the study within the first cycle of treatment for reasons other than adverse events, the subject will be replaced; and only DLTs occurring in Cycle 1 will be used for establishing safety during the run-in phase I study. However, all adverse event data will be summarized in the final analysis. For this run-in phase I study, DLT the study design is defined in Section 7.0. The patients treated at the MTD within the phase I will be included in the phase II efficacy analysis. Safety for all patients (including the patients in the run-in phase I study) will continue to be monitored via the Adverse Event Stopping Rule.

- 16.12 Sample Size: Phase I: The study may involve a maximum of 12 patients (6 for each of 2 dose levels). Phase II: This study will accrue an additional 35 patients to have a total of 41 patients accrued to the efficacy portion of this study (6 patients at the MTD in the phase I portion plus 35 patients accrued during the phase II portion). This includes 10% overaccrual of patients during the phase II portion to allow for cancellation, ineligibility, and major treatment violations (i.e., accrual of 41 patients to have 37 evaluable patients as required in 16.41). Overall: Therefore, overall, the study will accrue a maximum of 47 patients.
- 16.13 Accrual Time and Study Duration: The anticipated accrual rate is approximately 2 patients per month, based on physician estimate. This corresponds to a requirement of approximately 17 weeks to enroll (12 weeks), treat (4 weeks), and evaluate (1 week to submit data) 6 patients. Therefore, the accrual time for the phase I portion will be a maximum of 34 weeks. The overall study duration will be 34 weeks (phase I component) + 70 weeks (accrual of an additional 35 patients) + 16 weeks (4 months to evaluate the primary endpoint) = 120 weeks (about 28 months). The final analysis can begin approximately 28 months after activation, i.e., as soon as the last patient has been observed for 4 months and data have been submitted.

16.14 Operating Characteristics: The following table gives the probability of dose escalation at a single dose level as a function of the true probability of DLT at that level using the cohorts of 3 design described in Section 7.0.

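### The closed DLT list in 7.213 leaves out related deaths and Grade 4 events of unlisted types, so the written escalation rule ignores them

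*Combined protocol and SAP*

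**What the plan says.** Section 7.213 requires "an adverse event attributed (definitely, probably, possibly) in the first cycle to the study treatment and meeting the following criteria". The criteria are Grade 4 neutropenia, Grade 4 thrombocytopenia, and Grade 3 or higher anaphylaxis, proteinuria, hematuria, acneiform rash, diarrhea or oral mucositis. One row of the table is empty in the text as extracted; it is read here as layout.

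Escalation depends on DLTs alone. Section 7.222 states: "If dose-limiting toxicity (DLT) is not seen in any of the 3 patients, 3 new patients will be accrued" and treated at the next level. Sections 7.223 and 7.224 continue in the same terms, and the MTD in 7.22 follows from them. Section 16.11 adds that "only DLTs occurring in Cycle 1 will be used for establishing safety during the run-in phase I study".

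On who counts, 16.11 says that to be evaluable "the subject must have received at least one dose of each drug in Cycle 1". Sirolimus is given "Daily (cycle 1 only, begin day 8" (7.11). Section 7.24 adds a further patient "If a patient fails to complete Cycle 1 for reasons other than toxicity", and 16.11 likewise replaces only withdrawals not due to adverse events.

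**The concern.** A related cycle 1 death, or a related Grade 4 non-hematologic event, of a type outside the list does not meet the DLT definition. These are events the protocol itself anticipates. Section 15.27 names sepsis, interstitial pneumonitis and pulmonary hemorrhage for sirolimus; 15.17 names interstitial pneumonitis for auranofin, as a rare event (<1%). Section 8.2 stops both drugs for pneumonitis of any grade, and 16.532 treats related Grade 4 or higher non-hematologic events as the safety signal for suspending accrual. The run-in rule gives the same events no weight.

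At stake are the step from 3 to 6 mg auranofin and the dose taken into phase II. One related fatal sepsis among the first three evaluable patients would, on the written rule, neither stop escalation nor add three patients at that dose. Any such step would rest on discretion.

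**Working it through.** **How such a patient is counted.** No section says this outright, so the sections have to be read together.

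1. The event is related and falls in cycle 1, but it is not on the 7.213 list. It is not a DLT.
2. The patient has had at least one dose of each drug, so is evaluable under 16.11.
3. The patient was lost to toxicity, so neither 7.24 nor 16.11 provides a replacement.
4. The patient therefore stays in the denominator without a DLT, and 0 of 3 leads to escalation under 7.222.

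The point is limited in three ways. Fatal events of the six listed non-hematologic terms already count, because those entries start at Grade 3. Sepsis with related Grade 4 neutropenia counts through the neutropenia. A patient lost before the first sirolimus dose on day 8 is not evaluable.

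**Reproducing the plan's figures.** Under 7.222 and 7.223, escalation follows 0 of 3, or 1 of 3 and then 0 of 3 more. With true DLT rate p:

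f(p) = (1−p)³ + 3p(1−p)² × (1−p)³ = (1−p)³ + 3p(1−p)⁵

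For p = 0.1, 0.2, 0.3, 0.4, 0.5 this gives 0.906, 0.709, 0.494, 0.309, 0.172. The table in 16.14 has 0.91, 0.71, 0.49, 0.31, 0.17, so it is reproduced.

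**Effect of counting the unlisted events.** The only documented rate is <1% for auranofin pneumonitis, so the inputs are assumptions: listed DLTs at 10%, and unlisted related Grade 4–5 events at rate u, independent of the listed ones.

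- Combined rate: p = 1 − 0.90 × (1−u)
- At least 1 of 3 patients with an unlisted event: 1 − (1−u)³
- Escalation straight after 3 patients despite such an event: 0.9³ × [1 − (1−u)³], where 0.9³ = 0.729
- Expected patients at a level: 3 + 3 × 3p(1−p)²

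| u | p | f(p) | 1 − f(p) | ≥1 of 3 unlisted | Escalates straight after 3 despite it | Expected patients |
|---|---|---|---|---|---|---|
| 0 | 0.100 | 0.906 | 0.094 | 0 | 0 | 3.73 |
| 0.01 | 0.109 | 0.891 | 0.109 | 0.030 | 0.022 | 3.78 |
| 0.05 | 0.145 | 0.824 | 0.176 | 0.143 | 0.104 | 3.95 |
| 0.10 | 0.190 | 0.730 | 0.270 | 0.271 | 0.198 | 4.12 |

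As written, the rule escalates with probability 0.906 whatever u is.

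**Sensitivity.** For u = 0, 0.01, 0.05, 0.10:

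- listed DLTs at 5%: f = 0.973, 0.963, 0.910, 0.824
- listed DLTs at 20%: f = 0.709, 0.691, 0.622, 0.536
- rates added instead of combined independently (listed at 10%): f = 0.906, 0.889, 0.814, 0.709

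**Whether 16.532 fills the gap.** It is headed as phase II only, but 16.11 extends it to run-in patients. It needs 3 affected patients. After the first cohort with no listed DLT, all three would have to have an unlisted event. The chance that all three do is u³ = 0.000001, 0.000125 or 0.001.

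**The case against.** The strongest defense is that the list is aimed at the drug being escalated. Only auranofin changes dose, sirolimus is fixed at 5 mg, and most listed terms match auranofin's profile in 15.17, whereas sepsis and pulmonary hemorrhage appear only under sirolimus. The protocol does not give this rationale. It could justify leaving out some Grade 3 terms. It does not justify giving no weight to a death judged related to a combination whose joint tolerability is the question.

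Second, other safeguards exist. Accrual pauses during cohort observation ("accrual will be suspended while the 3 patients are treated and observed"), 10.2 requires written reports of Grade 3 to 5 events within 5 working days, 8.2 acts in the affected patient, 16.43 takes adverse events into account in any decision to terminate, the DSMB reviews safety at least twice a year, and 16.532 allows discretionary suspension. A related death would very probably be looked at quickly. That stands, but none of these changes the DLT count.

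Third, 7.211 and 7.221 ask for at least one cycle of observation, so a patient who dies in cycle 1 arguably leaves the 0-of-3 condition unmet. This reading is possible. However, 16.11 defines evaluability by doses received, and no section provides a replacement after toxicity. The ambiguity is itself a reason to write the rule down.

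Fourth, the larger effects need event rates of 5% or 10% that nothing in the documents supports. That is correct: at 1% the change is small.

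Finally, attribution includes possible relatedness, and ECOG 2 patients with advanced lung cancer are eligible, so a wider definition could count some disease-related infections or bleeds. That is a real cost of the change.

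**Conclusion.** The concern holds. Related deaths and related Grade 4 non-hematologic events of unlisted types have no weight in the written escalation rule when they occur in an evaluable patient. This follows from 7.213, 7.222 to 7.224, 7.24 and 16.11 read together and does not depend on any assumed rate. The size does: under the illustration (listed DLTs at 10%, unlisted events independent at 1%, 5% or 10%), the chance of escalating straight past such an event is 0.02, 0.10 or 0.20. The escalation probability would fall from 0.91 to 0.89, 0.82 or 0.73 if the events counted. The 16.14 table is correct as a function of the true DLT rate. This is a design choice that should be changed, held with medium confidence because the practical effect depends on unknown rates and on how far discretion would fill the gap.

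**What to change.** Add two rows to the 7.213 table:

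- any death at least possibly related to study treatment;
- any related Grade 4 or higher non-hematologic event, with exceptions (such as asymptomatic lipid elevations) stated.

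The second row uses the category already in 16.532. Whether to count other unlisted Grade 3 events, non-fatal Grade 4 anemia, or events below Grade 4 that lead to discontinuation under 8.2 (for example low-grade pneumonitis) is the sponsor's clinical choice. The 16.14 table needs no change.

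The cost is a one-table amendment and a lower chance of escalating. Section 7.21 has no level below 0, so at the starting dose the chance of finding no acceptable dose rises from 0.09 to 0.11, 0.18 or 0.27 under the same assumptions. These figures leave out the 7.224 path in which level 0 passes at 0 of 3, level 1 fails, and level 0 then fails on expansion. With the same rate at both levels, that path has probability (1−p)³ × [1−f(p)] × P(at least 2 of 3); at p = 0.19 this is 0.531 × 0.270 × 0.095 = 0.014. Expected patients at a level rise from 3.7 to 3.8, 4.0 or 4.1. The phase I maximum of 12 does not change, and the events are already collected.

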7.22 MTD Determination

MTD is defined as the dose level below the lowest dose that induces doselimiting toxicity in at least one-third of patients (at least 2 of a maximum of 6 new patients).

7.221 Three patients will be treated at a given dose level combination and observed for at least 1 cycle to assess toxicity (accrual will be suspended while the 3 patients are treated and observed).

- 7.222 If dose-limiting toxicity (DLT) is not seen in any of the 3 patients, 3 new patients will be accrued and treated at the next higher dose level. If DLT is seen in 2 or 3 of 3 patients treated at a given dose level, then the next 3 patients will be treated at the next lower dose level, if only 3 patients were enrolled and treated at this lower dose level.
- 7.223 If DLT is seen in 1 of 3 patients treated at a given dose level, up to 3 additional patients will be enrolled and treated at the same dose level (accrual will be suspended while the 3 patients are treated and observed). If DLT is seen in at least one of these additional three patients (≥2 of 6), the MTD will have been exceeded and further accrual will cease to this cohort. If DLT is not seen in any of the three additional patients, 3 new patients will be accrued and treated at the next higher dose level.
- 7.224 After enrolling 6 patients on a specific dose level, if DLT is observed in at least 2 of 6 patients, then the MTD will have been exceeded and defined as the previous dose unless only 3 patients were treated at the lower dose level. In that case, 3 additional patients will be treated at this lower dose level.
- 7.23 Dose Escalation: Doses will not be escalated in any individual patient.
- 7.24 If a patient fails to complete Cycle 1 for reasons other than toxicity, the patient will be regarded as treatment intolerant and an additional patient will be treated at the current dose level.
- 7.3 Patients can be instructed in administration techniques for both sirolimus and auranofin and granted treatment independence.
- 7.4 Patient must return to Mayo Clinic for evaluation at least every week during the first cycle of treatment and then at least every 4 weeks.
- 7.5 Study treatment by a local medical doctor (LMD) is not allowed.

8.0 Dosage Modification Based on Adverse Events

Strictly follow the modifications in this table for the first **two** cycles, until individual treatment tolerance can be ascertained. Thereafter, these modifications should be regarded as guidelines to produce mild-to-moderate, but not debilitating, side effects. If multiple adverse events are seen, administer dose based on greatest reduction required for any single adverse event observed. Reductions or increases apply to treatment given in the preceding cycle and are based on adverse events observed since the prior dose.

ALERT: ADR reporting may be required for some adverse events See Section 10

8.1 Dose Levels (Based on Adverse Events in Tables 8.2)

| Dose Level | Auranofin | Sirolimus |
|---------------|---------------|----------------|
| +1 | 6 mg po daily | Not applicable |
| 0 | 3 mg po daily | 5 mg po daily |
| -1 | 3 mg po qOd | 3 mg po daily |
| -2 | None | 2 mg po daily |

8.2 Dose modification Table

| ☐ ☐ Use the NCI Common Terminology Criteria for Adverse Events (CTCAE) version | | | |
|--|---------------|-------|--------|
| 4.0* unless otherwise specified \square | | | |
| CTCAE System/Organ/ Class (SOC) | ADVERSE EVENT | AGENT | ACTION |
| BASED ON INTERVAL ADVERSE EVENT | | | |

| □ □ Use the N | CI Common Terminolog 4.0* unless o | | or Adverse Events (CTCAE) version |
|--|--|------------------------|---|
| CTCAE System/Organ/ Class (SOC) | ADVERSE EVENT | AGENT | ACTION |
| Investigations | Neutrophil count decreased Grade 4 Platelet count decreased Grade 4 | Auranofin Sirolimus | Delay therapy until ANC ≥ 1500 and/or PLT ≥ 100,000, and decrease by 1 dose level; discontinue treatment if toxicity persists beyond 14 days or if subject is already at dose level -2 and go to event monitoring phase per Section 18. |
| | Neutrophil count decreased Grade 3 Platelet count decreased Grade 3 | | Delay therapy until ANC ≥ 1500 and/or PLT ≥ 100,000. If delay is 1 week or less, resume at prior dose. If delay exceeds 7 days but is not more than 14 days, decrease by 1 dose level; discontinue treatment if toxicity persists beyond 14 days or if subject is already at dose level -2 and go to event monitoring phase per Section 18. |
| | Cholesterol High Grade 2 | | Institute appropriate lipid/cholesterol lowering therapy. Hold treatment until levels return to Grade 1. If unresolved by four weeks, discontinue auranofin and sirolimus therapy and go to event monitoring. |
| | Grade 3-4 | | Discontinue auranofin and sirolimus and go to event monitoring. |
| Respiratory, thoracic and mediastinal disorders | Interstitial pneumonitis any grade | Auranofin Sirolimus | Discontinue and go to event monitoring |

| \Box Use the NCI Common Terminology Criteria for Adverse Events (CTCAE) version 4.0* unless otherwise specified \Box \Box | | | |
|---|---------------------------------|------------------------|---|
| CTCAE System/Organ/ Class (SOC) | ADVERSE EVENT | AGENT | ACTION |
| Metabolism and nutrition disorders | Hypertriglyceridemia Grade 2 | Auranofin Sirolimus | Institute appropriate lipid/cholesterol lowering therapy. Hold treatment until levels return to Grade 1. If unresolved by four weeks, discontinue auranofin and sirolimus therapy and go to event monitoring. |
| | Grade 3-4 | | Discontinue auranofin and sirolimus and go to event monitoring. |
| Other non- hematologic adverse events | Non-hematologic Grade 3 or 4 | Auranofin Sirolimus | Delay therapy until severity decreases to grade 0-1 and decrease dose by one level; discontinue treatment if toxicity persists beyond 14 days or if subject is already at dose level -2 and go to event monitoring phase per Section 18 |

^{*} Located at http://ctep.cancer.gov/protocolDevelopment/electronic applications.ctc.htm

NOTE: Adverse events requiring a dose-reduction step for any or all drugs beyond the two dose-reduction steps (levels -1 and -2) will result in the patient coming off study.

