14.0 Body Fluid Biospecimens: None

15.0 Drug Information

15.1 Auranofin for Oral Administration (Ridaura®)

- 15.11 **Background**: Auranofin is a gold compound which has antiinflammatory effects. Gold compounds can alter the immune response and have been shown to inhibit prostaglandin synthesis.
- 15.12 **Formulation**: Commercially available for oral administration as: Capsules: 3 mg [gold 29%]

- 15.13 **Preparation, storage, and stability**: Refer to package insert for complete preparation and dispensing instructions. Store oral tablets at room temperature. Dispense in a tight, light-resistant container.
- 15.14 **Administration:** Refer to the treatment section for specific administration instructions.

15.15 Pharmacokinetic information:

Absorption: ~25% of the gold in a dose of Auranofin is absorbed from the gastrointestinal tract

Protein binding: Moderate. In blood, approximately 60% of the gold is bound to plasma proteins; the remainder is present in red blood cells

Metabolism: Rapidly metabolized (the intact molecule has not been detected in blood)

Half-life elimination: Blood: 21 - 31 days. Tissue: 42 - 128 days **Excretion**: 60% of the absorbed gold (15% of the administered dose) is excreted in the urine; the remainder of the dose is excreted in the feces

15.16 Potential Drug Interactions:

In a single patient-report, there is the suggestion that concurrent administration of Auranofin and phenytoin may have increased phenytoin blood levels.

15.17 **Known potential adverse events:** Consult the package insert for the most current and complete information. Auranofin is contraindicated in patients with a history of any gold-induced disorders: anaphylactic reactions, necrotizing enterocolitis, pulmonary fibrosis, exfoliative dermatitis, bone marrow aplasia or other severe hematologic disorders.

Common known potential toxicities, > 10%:

Dermatologic: Dermatitis (aggravated by sunlight), pruritus, actinic rash, hair loss, urticaria

Gastrointestinal: Nausea, vomiting, abdominal cramps, diarrhea, loose stools, constipation, dysgeusia, stomatitis, glossitis Hematologic: Anemia, leukopenia, thrombocytopenia, Eosinophilia

Hepatic: Elevated liver enzymes

Renal: Hematuria

Less common known potential toxicities, 1% - 10%:

Gastrointestinal: Anorexia, flatulence, dyspepsia

Ocular: Conjunctivitis Renal: Proteinuria

Rare known potential toxicities, <1% (Limited to important or life-threatening):

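### From auranofin level 0 or +1, Table 8.2 puts the patient back on auranofin at a lower dose after a resolved Grade 3-4 anaphylaxis, exfoliative dermatitis or necrotizing enterocolitis, against the contraindication in 15.17

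*Combined protocol and SAP*

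**What the plan says.** Table 8.2 has specific rows for neutrophils, platelets, cholesterol, interstitial pneumonitis and hypertriglyceridemia. Every other Grade 3 or 4 non-hematologic event goes to a catch-all row that applies to both drugs and has no condition on attribution. Its instruction is "Delay therapy until severity decreases to grade 0-1 and decrease dose by one level". Its only stopping conditions are these: "discontinue treatment if toxicity persists beyond 14 days or if subject is already at dose level -2".

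Section 8.0 sets the force of the table: "Strictly follow the modifications in this table for the first" two cycles. After that it is softer: "Thereafter, these modifications should be regarded as" guidelines.

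Section 8.1 gives auranofin 6 mg daily at level +1, 3 mg daily at level 0 and 3 mg every other day at level -1. At level -2 the auranofin and sirolimus entries read "None | 2 mg po daily".

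Section 15.17 says: "Auranofin is contraindicated in patients with a history of any gold-induced disorders: anaphylactic reactions, necrotizing enterocolitis, pulmonary fibrosis, exfoliative dermatitis". The list there goes on to marrow aplasia and other severe hematologic disorders.

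**The concern.** A patient who has had one of these reactions from auranofin on study has the history that 15.17 describes. The dose table then tells the investigator to give the drug again at a lower dose, while the drug-information section says it should not be given. Nothing in the protocol ranks the two texts.

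What is at stake is patient safety: re-exposure after a severe reaction that can be life-threatening when it recurs. In cycles 1-2 the table is to be followed strictly, so an investigator who declines to re-treat is the one departing from it.

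No endpoint, sample size or analysis is affected. The point does not extend to Grade 1-2 events, cytopenias, marrow aplasia or pulmonary fibrosis.

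**Working it through.** **Step 1: which row applies.** None of the specific rows in 8.2 covers anaphylaxis, exfoliative dermatitis or necrotizing enterocolitis. A Grade 3-4 event of any of the three is therefore handled by the catch-all row.

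**Step 2: where that row leads.** Take an event that falls to grade 0-1 within 14 days and read one level down in 8.1:

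| Level at the event | Auranofin before | Auranofin after one step down |
|---|---|---|
| +1 | 6 mg daily | 3 mg daily |
| 0 | 3 mg daily | 3 mg every other day |
| -1 | 3 mg every other day | none |
| -2 | none | treatment discontinued |

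Auranofin comes back from levels +1 and 0 only. The two Phase I doses in 7.21 (3 mg and 6 mg daily) are these two levels, so patients start where the row re-gives the drug. From level -1, or if the event lasts beyond 14 days, there is no conflict.

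**Step 3: whether another provision overrides the row.**

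- *15.191* tells nurses to withhold the drug and inform the study team. Withholding is also the first step of the catch-all row, and 15.191 does not forbid a later restart.
- *7.212*: "Investigators are to contact the Study Chair as soon as any dose-limiting toxicity occurs". Under 7.213 a DLT must be an event attributed "in the first cycle to the study treatment and meeting the following criteria". The list names anaphylaxis but neither exfoliative dermatitis nor enterocolitis, and contacting the chair does not alter the dose rule.
- *10.2* requires a written report within five working days. That is a report and not a stop.
- *Section 13* routes patients who leave treatment for reasons other than progression, but does not order them to leave.
- *Sections 3.2 and 9* contain no rule on the matter.

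By contrast, 8.2 does end both drugs outright for interstitial pneumonitis of any grade and for Grade 3-4 cholesterol or triglyceride elevation. The table can carry a permanent stop; it lacks one for these events.

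**Step 4: how often this could arise.** The protocol has no figure of its own to reproduce. Inputs:

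- *n* = 47, the maximum accrual in 16.12.
- *p* = event rate per type. Section 15.17 puts generalized exfoliative dermatitis below 1% and gives no rate for anaphylaxis or necrotizing enterocolitis. Assumed: 0.1%, 0.5% and 1%.
- *f* = share of events that are Grade 3-4, resolve within 14 days and occur at level 0 or +1. Assumed: 25%, 50% and 100%; the documents give no figure.

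With *q* = *p* × *f*, the expected number is 47*q* and the chance of at least one is 1 - (1 - *q*)^47.

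| *p* | *f* | Expected patients | Chance of at least one |
|---|---|---|---|
| 0.1% | 25% | 0.012 | 1.2% |
| 0.1% | 50% | 0.024 | 2.3% |
| 0.1% | 100% | 0.047 | 4.6% |
| 0.5% | 25% | 0.059 | 5.7% |
| 0.5% | 50% | 0.118 | 11.1% |
| 0.5% | 100% | 0.235 | 21.0% |
| 1% | 25% | 0.118 | 11.1% |
| 1% | 50% | 0.235 | 21.0% |
| 1% | 100% | 0.47 | 37.6% |

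The rows with *f* = 100% are upper bounds for their *p*. Counting only cycles 1-2 would lower every row.

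**The case against.** The strongest reply is that a specific contraindication should prevail over a residual row, and that 15.191 points the same way by sending the case to the study team. The catch-all row also never uses the word resume, as the Grade 3 cytopenia row does. This is a possible reading, but it has to be inferred against an instruction to follow the table strictly. An order to wait for recovery and then lower the dose by one level has no meaning unless dosing continues.

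Second, 15.17 refers the reader to the package insert, which may direct permanent discontinuation. That cannot be checked from the documents, and it would not correct the table.

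Third, the reach is narrow. Section 15.15 gives a blood half-life of 21 to 31 days, so at day 14 between 2^(-14/21) = 63% and 2^(-14/31) = 73% of the gold in blood would remain. Severe dermatitis or enterocolitis may well not settle within 14 days, and if it does not, the row itself stops treatment. In cycle 1, anaphylaxis is a DLT and goes to the Study Chair, as would an enterocolitis presenting as Grade 3 or worse diarrhea. After cycle 2 the table is only a guideline. All of this stands and lowers the expected number of cases; none of it changes the rule as written.

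Fourth, 15.17 is broader than three disorders at Grade 3-4, so a row limited to them does not align the whole protocol with it. That is fair, and a wider option is given under the fix.

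Finally, most oncologists would not re-treat after such a reaction, and the report within five working days makes an unreviewed restart less likely. Both are probably true, but the safe action should not be the one that departs from the protocol.

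**Conclusion.** The conflict is real. For a patient at level +1 or 0 whose Grade 3-4 anaphylaxis, exfoliative dermatitis or necrotizing enterocolitis is gold-induced and falls to grade 0-1 within 14 days, 8.2 leads to renewed auranofin and 15.17 contraindicates it. In cycles 1-2 the table is binding.

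Fewer than 0.5 patients per event type are expected in the whole trial: 0.01 to 0.47, with a 1% to 38% chance of at least one. This depends on the assumed rates and qualifying shares above; the 25% floor on the share is itself arbitrary, so 0.01 is not a true minimum. The dose path and the conflict between the sections do not depend on these assumptions. It must be fixed because of what could happen to the patient concerned, despite the small numbers.

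**What to change.** Add one row to Table 8.2, for example: *Anaphylactic reaction, exfoliative dermatitis or necrotizing enterocolitis, Grade 3-4, at least possibly related to auranofin: stop auranofin permanently; this row takes precedence over the one for other non-hematologic events.* Cross-reference it from 15.17 and 15.191.

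The row should also state the action for sirolimus, which is the sponsor's choice. Section 15.17 concerns auranofin only, and level -2 already allows sirolimus alone; on the other side, 15.27 lists hypersensitivity among the sirolimus toxicities.

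As an optional extension, a sentence in 8.0 could say that the contraindications in 15.17 override Table 8.2. That would also cover the disorders and grades outside this point.

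The cost is one table row and two cross-references in an amendment, with no added patients, visits or procedures. The downside is that a rare patient (fewer than 0.5 expected per event type) loses auranofin, and sirolimus too if the sponsor stops both, although he or she might have tolerated it.
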